4.2 Primary Implementation Outcomes

4.2.1 –Initial Pilot Training

Fidelity. At least one session or roleplay per CHW ($n = 25$) will be rated for fidelity using the fidelity monitoring tool. If a CHW recorded more than one session with a patient, the recording to be assessed for fidelity will be randomly selected. If the session or roleplay to be rated is conducted in English, the independent fidelity rater will rate the session as they listen to the audio. If the session is not conducted in English, it will be translated into English and then rated for fidelity using the checklist. Fidelity monitoring will focus on the presence of stigmatizing language and behaviors, adherence and competence in delivering skills learned in training, correct information, and the presence of positive, supportive interactions (i.e., use of positive affirmations in steps towards change). A final fidelity score will be calculated for each rated session/roleplay based on the proportion of key intervention components delivered as attended across interactions based upon these ratings.

4.1.2 Stepped-Wedge Trial

Fidelity. ENACT roleplays at the 3MFU will be rated for fidelity using a predetermined fidelity checklist. If the roleplay to be rated is conducted in English, an English-speaking

independent fidelity rater will rate the session as they listen to the audio. If the session is conducted in isiXhosa, an isiXhosa-speaking independent fidelity rater will rate the session using the same checklist (translated into isiXhosa). Fidelity monitoring will focus on the presence of stigmatizing language and behaviors, adherence and competence in delivering skills learned in training, correct information, and the presence of positive, supportive interactions (i.e., use of positive affirmations in steps towards change). A final fidelity score will be calculated for each rated session/roleplay based on the proportion of key intervention components delivered as attended across interactions based upon these ratings.

Feasibility. Feasibility will be assessed by assessing CHW attendance in the training. Over 75% of training sessions attended across all CHWs will be used a threshold for determining feasibility based on our prior work. Feasibility will additionally be assessed using the Feasibility subscale of the D&I tool.⁴⁸ CHWs will complete this measure at the 3MFU (primary) and 6MFU (secondary). Further, we will convergently analyze the quantitative measure of feasibility collected from CHWs with the qualitative exploration of feasibility among CHWs. The coding process will be aided by the CFIR codebook and coding tool (available at <http://cfirguide.org>). After coding the individual transcripts, we will create case memos, which summarize, aggregate, and prioritize the barriers by CFIR construct and implementation outcomes for each participant. This will identify the most prevalent implementation barriers that require implementation strategy prioritization. Key themes from qualitative interviews with CHWs will then be compared for discrepancies and areas of alignment with the quantitative measure from CHWs. Lastly, key themes from qualitative interviews with stakeholders will also be compared to findings from CHWs for areas of discrepancy and alignment and for further organizational context.

Acceptability. Acceptability will be assessed using the Acceptability subscale of the D&I Tool,⁴⁸ which measures the perceived satisfaction, relevance, usefulness, comprehension, and comfort level of the training to the CHWs. Acceptability will be assessed at both the 3MFU (primary) and 6MFU (secondary). We will also convergently analyze the quantitative acceptability measure collected from CHWs with qualitative data on acceptability from CHWs, using the same methods as for feasibility. Again, we will also compare and contextualize the mixed-methods data from CHWs with qualitative data from stakeholders.

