1.2.2 Stepped-Wedge Pilot Trial

To further evaluate the implementation (feasibility, acceptability, fidelity) and preliminary effectiveness of this CHW training program to reduce CHW stigma towards depression and SU in order to promote re-engagement in TB/HIV care, we will conduct a Type 2, hybrid effectiveness-implementation trial.¹ This will be guided by Proctor's implementation model.² Using a stepped-wedge design with multiple NGO/clinic sites ($N = 60$ CHWs total), we will randomly allocate the timing of the CHW training (versus treatment as usual; TAU) over six months. The following multi-level outcomes will be evaluated:

- a. Feasibility, acceptability and fidelity of the CHW training (primary implementation outcomes). This will be assessed through both quantitative and qualitative methods so that qualitative data can add key context to quantitative findings and will include both CHWs and stakeholders (e.g., NGO leaders, policymakers focused on CHW training, supervisors of CHWs) to identify potential organizational barriers and facilitators to implementation of the training beyond the course of this study.
- b. CHW stigma towards depression and SU in TB/HIV patients (primary; effectiveness outcome)
- c. Patient re-engagement in TB/HIV care over six months via chart review (secondary effectiveness outcome)

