Patients who agree to be contacted by a researcher and complete informed consent will be given a brief assessment where they are asked about demographic information, their HIV and/or TB, depression, and substance use. They will also be asked about their thoughts on their most recent CHW visit. Please note that informed consent will including consenting to the Protection of Personal Information Act 4 of 2013.

3.5.1f CHW Fidelity

CHW fidelity to the training will be measured in either or both of the following ways: through audio-recordings with real patients and through role-playing after the training.

- a) Audio-recordings with patients. Audio-recordings obtained by the CHWs will be assessed for fidelity to the training (i.e., skills taught that the CHW uses, correct information, and non-judgmental language). If a CHW obtains multiple audio-recordings, one audio-recording will be randomly selected to be assessed for fidelity.
- b) Roleplays. The roleplays in the post-assessment training will be videorecorded and will also be rated for fidelity to the training (i.e., skills taught that the CHW uses, correct information, and non-judgmental language, including non-judgmental nonverbal communication). Using roleplay information will (1) allow us to assess fidelity immediately after the training and (2) allow us to assess fidelity to the training even if CHWs are unable to later obtain audio-recordings of their actual sessions with patients.

3.5.1g CHW Supervision

Once a week for about a month, each CHW will have the opportunity to receive weekly small group supervision (n=5) with a registered psychological counselor. Supervision sessions will include feedback from fidelity checks, reminders from the three-day training, and role-playing of challenging patient interactions. There

will also be opportunities for clinical debriefing and psychosocial support for challenging patient interactions with a focus on problem solving. Role-plays may also be recorded at the end of some supervision sessions.

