3.5.2 Stepped Wedge Trial

3.5.2a CHW Screening & Consent

Potentially eligible CHWs—referred to us by NGO staff will be screened for eligibility. If eligible and interested in participating, they will undergo informed consent procedures. As part of this process, participants will be informed of all the potential risks and benefits to taking part in the study. Participants will be reminded that participation is voluntary, that they can decline to answer any questions they are not comfortable answering, they can leave the study at any point, and their decision to participate in the study will not impact their job. As part of signing the consent form, they will also consent to the Protection of Personal Information Act 4 of 2013.

3.5.2b CHW Baseline and Pre-Training Assessments

Baseline Assessment. Upon giving willing, informed consent, CHWs will complete a baseline assessment with study staff. The baseline assessment will consist of self-report questions around CHWs' demographic characteristics and job, personal mental health questions, questions around knowledge of HIV, TB, depression and substance use, and questions around stigma.

Pre-Treatment Assessment. Immediately before their training, participants will complete a pre-training assessment. At this visit, participants will be asked to answer the same self-report questionnaires and as they did at baseline (with the exception of demographic and job information, which will not be asked again). All CHWs will also complete a brief (~10 minutes) role-play vignette with a staff member who is minimally involved in delivering the training, which will be videotaped and later coded for stigma using the ENACT.

3.5.2c CHW Training

After the baseline assessment all groups will receive at least one dose of TAU. Based on the training time to which their cluster was randomized, CHWs will then be invited to participate in a training on mental health and substance use.

Clusters randomized to Training Time #1 will receive the training first (while the other training times continue to receive TAU), followed by Training Time #2 (while the final training time continues to receive TAU), and finally, Training Time #3.

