4.1 Type and purpose of Data

4.1.1 Initial Pilot Training

As this is a pilot of our training, the main purpose of data collection is for us to collect sufficient information that will allow us to adapt the training for the next phase (implementation of training across six clinics). The aim of the study is not to generate effect sizes or statistical significance but rather pilot procedures including data collection procedures with patients who interact with CHWs) and gather feedback on how well these procedures worked and how they might need to be refined for the future.

This study will collect quantitative and video data from assessments with CHWs ($n = 25$) and brief assessments with their patients ($n = 75$). CHW fidelity to training will also be generated by having an independent team member listen to a subset of sessions and/or roleplays and rate the sessions on a pre-determined fidelity checklist.

Conducting roleplays both at the assessments before and after the training will also allow us to measure improvements in competencies we teach in the training (i.e., non-judgmental communication, confidentiality). If the roleplay is conducted in English, the independent rater will rate the video as they watch the video. If the session is not conducted in English, it will be translated into English and then rated along with the non-verbal communication from the video. A final competency score^{45,46} will be calculated for both pre-training and post-training roleplays for comparison.

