Recordings. With the permission patients, some CHW sessions will be audio recorded for analysis. Please note that because CHWs—not patients—are the focus of these recordings, patients will not be enrolled in the study if their session is audio recorded. They will only be enrolled in the study if they choose to participate in a brief assessment about themselves and their CHW's visit. Roleplays with CHWs and either another CHW or staff member will be videorecorded. Qualitative interviews will be audio-recorded. If a roleplay, interview, or session is translated (e.g., because it is conducted in a non-English language), the translator will be a member of the study team and will leave out any potentially identifying data (e.g., names, locations). Roleplays will be recorded at the time of the training and saved in a secure location that only study-staff can access (i.e., UMD Box) and saved with the CHW's study ID. Qualitative interview recordings will also be stored in a secure location that only study-staff can access (i.e., UMD Box) and saved with the participant's study ID. CHWs will receive verbal consent from their patients before recording a normal session. If the patient does not want their session recorded, the visit will continue as usual. During training and supervision we will stress to CHWs that it is okay if none of their patients want to be recorded. If a session is recorded, the CHW will be asked to let the study team know. The study team will pick up the recording device as soon as possible and upload it to a secure database using the study computer. The audio file will then be deleted from the digital recorder. Computer audio files will be saved in a secure location that only study-staff can access (i.e., UMD Box) and saved with the CHW's study ID. Following the South African good clinical practice (GCP) guidelines and guidelines set by the American Psychological Association (APA; APA Record Keeping Guidelines, Guideline #7), recordings will be maintained until seven years after the publication of the study.). The ethics committee will review study procedures at least annually to review procedures pertaining to participant confidentiality.

Identifiable Data. Consent forms and any other documents with identifiable information will be kept in a separate, secure filing cabinet at the secure SAMRC study site.

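### The fidelity rule for English 3-month roleplays in the stepped-wedge trial has raters listen to audio, although the roleplays are on video and the rating covers behaviour as well as language

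*Combined protocol and SAP*

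**What the plan says.** Section 1.2.2 lists "Feasibility, acceptability and fidelity of the CHW training (primary implementation outcomes"), so fidelity stands among the main results of the stepped-wedge trial.

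The scoring rule is the fidelity paragraph headed 4.1.2 Stepped-Wedge Trial, which falls under 4.2, Primary Implementation Outcomes. It takes the roleplays from the 3-month follow-up (3MFU).

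- **English roleplays:** an English-speaking "independent fidelity rater will rate the session as they listen to the audio".
- **isiXhosa roleplays:** "If the session is conducted in isiXhosa, an isiXhosa-speaking independent fidelity rater will rate the session using the same checklist (translated into isiXhosa"). Neither sound nor picture is mentioned.
- **Content of the rating:** "Fidelity monitoring will focus on the presence of stigmatizing language and behaviors". It also covers skills, correct information and supportive interaction.
- **Score:** the proportion of key components delivered as planned.

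On the recordings, Section 6.1.1 gives the general rule: "Roleplays with CHWs and either another CHW or staff member will be videorecorded". For the stepped-wedge pre-training roleplay, Section 3.5.2b adds "which will be videotaped and later coded for stigma using the ENACT".

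**The concern.** A rater who only listens can judge words and tone but not posture, gaze or other visible conduct. The fidelity paragraph separates behaviour from language and wants both covered, so its rating instruction does not match the content it is meant to measure. This matters because the training aims to reduce stigma, and conduct towards the patient is central to that aim.

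There are two consequences. First, any checklist component that can only be seen has to be left out, guessed, or given a default value in an English roleplay, and the plan does not say which. Second, a medium is stated for one language only. If isiXhosa raters watch the video while English raters listen, the two sets of scores are produced differently. With so few rated roleplays, that difference could not be separated from a real difference between CHWs.

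**Working it through.** There is no stated figure to reproduce. The check is a comparison of sections, followed by the number of roleplays affected and a test of whether a direction of bias can be claimed.

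**1. Is there a picture to rate?** Yes, as planned. Section 6.1.1 has roleplays videorecorded, Section 3.5.2b says so for the pre-training roleplay, and the stepped-wedge paragraph on type and purpose of data (also numbered 4.1.2, under 4.1) says video data are collected. The 3MFU text in Section 3.5.2d does not name the medium, so video at that visit rests on the general rule.

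**2. Does the plan treat visible conduct as part of fidelity?** Yes, in the pilot. Section 3.5.1f rates videorecorded roleplays for fidelity, "including non-judgmental nonverbal communication". Section 4.1.1 has "the independent rater will rate the video as they watch the video" for English roleplays, but those ratings feed a competency score, so this supports the point only indirectly.

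**3. Where might the audio wording come from?** Section 4.2.1 uses the same wording for the pilot, where audio recordings of patient sessions were among the material to be rated. The stepped-wedge trial rates no patient sessions, so that reason for audio has gone. Section 4.2.1 applies the wording to pilot roleplays too, so the pilot text is itself at odds with Section 3.5.1f.

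**4. Does another section settle the medium?** No. Section 6.1.2 has raters in each language review the recording on the study's storage platform, without saying whether they watch or listen.

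**5. How many roleplays are affected?** Section 3.5.2g samples 20% of 3MFU roleplays: 0.20 × 60 = 12 if all CHWs attend. Section 3.5.2c allows English or isiXhosa and gives no split, so the audio rule reaches 0 to 12 roleplays. The fidelity paragraph does not repeat the 20%; the count here relies on Section 3.5.2g.

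**6. Can a direction be claimed?** The checklist is not in the documents, so every input here is an assumption: 10 items, k = 1 to 3 of them visible only, visible items delivered at a rate p of 40% to 60%, and other items at 80%.

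- Video score: ((10 − k) × 0.80 + k × p) / 10. This gives 76–78%, 72–76% and 68–74% for k = 1, 2, 3.
- Audio, unseen items dropped: 80% for every k, which is 2 to 12 points above video.
- Audio, unseen items scored as not delivered: (10 − k) × 0.80 / 10 = 72%, 64%, 56%, which is 4 to 18 points below video.

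The sign depends on a handling rule that the plan does not give. Even when items are dropped, the gap is k × (0.80 − p) / 10, which reverses if visible items are delivered better than the rest.

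**The case against.** The strongest reply is that this is loose drafting and not an audio-only rule. The same words cover pilot roleplays in Section 4.2.1, although Section 3.5.1f has non-verbal conduct rated there. The sentence is mainly about matching the rater's language to the roleplay's. The stepped-wedge paragraph under 4.1 speaks of video data and of an independent team member rating the roleplays for both fidelity and ENACT stigma, and Section 6.1.2 describes one procedure for both languages. A carry-over is quite possible. Even so, the paragraph that defines the score tells the rater to listen, and no other stepped-wedge text tells the fidelity rater to watch.

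It is also fair to say that little hangs on the score. Fidelity has no benchmark (the 75% threshold is for attendance), no hypothesis test and no planned comparison by language. Some stigmatizing behaviour, such as scolding, can be heard. These points limit the weight of the concern but do not remove the inconsistency.

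A reader might infer three stronger things that the documents do not support.

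- **That non-verbal stigma goes wholly unscored.** The same roleplays receive a separate ENACT stigma rating (Sections 3.5.2d and 3.5.2g, and the stepped-wedge paragraph under 4.1). The documents do not list the ENACT items or say that its stepped-wedge raters watch the video, so its coverage of visible conduct is likely but not shown. As a separate score it does not repair fidelity.
- **That fidelity is overstated by some 2 to 12 points.** That range needs an invented checklist and one particular handling of unseen items; another handling reverses the sign.
- **That comparability with the pilot is broken.** Both fidelity sections carry the same audio wording, and no comparison with the pilot is planned.

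**Conclusion.** The inconsistency is real and narrow. The stated rating medium for English 3MFU roleplays does not fit the stated content of a primary implementation outcome, and the medium for isiXhosa roleplays is left open. Followed literally, visible stigmatizing behaviour cannot enter the fidelity score of the English roleplays in the 20% sample, and the scoring medium could differ by language.

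The conclusion rests on reading the audio instruction as written and on the general videorecording rule holding at the 3MFU. It does not depend on the illustrative percentages. The amendment is worth making before rating starts; the point does not threaten the trial's main stigma analysis, which uses the Social Distance Scale.

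**What to change.** In the stepped-wedge fidelity paragraph under 4.2, replace the audio instruction with one rule for both languages. For example: *Each selected 3MFU roleplay, whether in English or isiXhosa, is rated for fidelity from the video recording, with sound, by an independent rater who speaks that language; non-verbal behaviour is scored.* This agrees with Sections 3.5.1f, 6.1.1 and 6.1.2 and with the stepped-wedge paragraph under 4.1. If a recording has lost its picture, state how the visible items are handled and report how many roleplays are affected.

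The cost is one or two sentences. The videos are already planned and an independent team member already rates the roleplays for fidelity and ENACT, so no new data are collected. Left until after rating, the same correction would mean rating the English roleplays again.

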4.3 Primary Preliminary Effectiveness Outcomes (Stepped-Wedge Trial Only)

4.3.1 –Stepped Wedge Trial

CHW Stigma. The primary measure of CHW stigma is the Social Distance Scale (SDS),^{20,43,44} a well-validated measure of stigma used to capture health-related stigma across conditions and has been recommended for assessing mental health stigma among healthcare providers. A total SDS score will be calculated to represent CHW stigma towards the target population at each timepoint, with high scores indicating greater desire for social distance. First, we will conduct descriptive analyses (e.g., mean, standard deviation) to summarize the CHW stigma, using the continuous SDS score. The data distribution will be assessed to see whether the underlying assumptions are met (e.g., normality). To account for the stepped wedge study design, we will fit a linear mixed model (LMM). This analytic approach will allow us to account for both random effects of the clinic and CHW, and fixed effects of time and the effect of the training. We will analyze the within- and between-group effects. Specifically, the within group effect will evaluate changes in stigma before and after receiving the training with CHWs from the same clinic,

and the between group effect will compare the CHW training to assessments before the CHW training. An F-test will be used to test the between and within clinic intervention effects. Covariates (i.e, CHW demographic and job-related characteristics) will be included in the model. The model accounts for any baseline differences in CHW stigma between clinics and individual CHWs. Secondary measures of CHW stigma will include behavioral coding to stigmatizing responses in a role play based on vignettes using the ENACT scale.^{45,46,51} Specifically, we will examine whether specific ENACT items (interpersonal skills sub-scale) at the pre-training timepoint predict other ENACT items (clinical skills sub-scale) at the later timepoints using multivariate linear models. This will allow us to begin to explore whether pre-training ENACT roleplays could be helpful for pre-training screening of CHWs in future research. We will also examine improvement in individual ENACT items across the data collection timepoints to examine the effect of the training and supervision on CHW helping skills and the durability of CHW helping skills over time. Additionally, analyses will be conducted on the an integrated HIV and TB stigma scale to measure intersectional HIV and TB stigmas. This scale has previously been validated among health workers in SA.^{49,50}

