The training in the stepped-wedge trial will be the as the initial training, with minimal adaptations based on participant feedback (e.g., potentially an additional day, allocating more or less time to specific concepts, etc.). It will still be conducted in English, as all CHW trainings offered by the Western Cape Department of Health are required as part of the CHW certification occur in English. Roleplays will be conducted in English (training language) or isiXhosa (patients' language). Additionally, our training team consists of English, isiXhosa, and Afrikaans mother-tongue speakers; therefore, our team will be able to address questions and further explain concepts in these languages if needed.

3.5.2d CHW Post-Training Assessments

In addition to the Baseline and Pre-Treatment Assessments (which both occur before the training, and therefore, measure TAU), CHWs will also be required to complete two additional assessments after the training:

3-Month Follow-Up Assessment (3MFU): All participants will be invited to complete a follow-up assessment approximately 3-months after their training (3MFU). At this visit, participants will answer the same self-report questions they answered at the Pre-Training Assessment, answer additional questions about their perceived feasibility/acceptability of the training, and complete a roleplay for later ENACT coding.

6-Month Follow-Up Assessment (6MFU): All participants will also be invited to complete another follow-up assessment approximately 6-months after their training (6MFU). At this visit, participants will answer the same self-report questions they answered at the 3MFU and complete a roleplay for later ENACT coding. A subset of CHWs will also participate in semi-structured individual interviews in which they answer open-ended questions about their perceived feasibility/acceptability of the training.

3.5.2e Additional CHW Self-Report Measures

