CHWs will complete the same measures during the stepped-wedge trial as they did in the initial training. In addition, they will also complete an integrated measure that assesses stigmas related to HIV and TB, which has been previously validated among health workers in South Africa.^{49,50} Additionally, the personal questions around personal mental health/ substance use will be slightly expanded upon (i.e., asking about self and friends in addition to family). Although there is not an immediate post-training assessment, participants will additionally do another roleplay on their last day of training, which will be rated using the ENACT.^{45,46} Please see Initial Training Procedures (above) for more information on the roleplay.

Based on feedback from the initial training, measures used in the initial training may also be shortened or slightly reframed (e.g., only asking the feasibility and acceptability subscales of the D&I measure).

3.5.2f Stakeholder Screening and Consent

Potentially eligible NGO leaders and stakeholders will be screened for eligibility. If eligible and interested in participating, they will undergo informed consent procedures. As part of this process, participants will be informed of all the potential risks and benefits to taking part in the study. Participants will be reminded that participation is voluntary, that they can decline to answer any questions they are not comfortable answering, they can leave the study at any point, and their decision to participate in the study will not impact their job. As part of signing the consent form, they will also consent to the Protection of Personal Information Act 4 of 2013.

3.5.2g Additional Measurements

Training Feasibility. CHW attendance in the training (less than one-week) and will be assessed as one measure of training feasibility. Over 75% of training sessions attending across all CHWs will be used as a benchmark for assessing whether the training is feasible.²

CHW Fidelity. To assess the fidelity of CHW delivery of training components (e.g., using non-judgmental communication, implementing MI/PST skills), 20% of the 3MFU roleplays will be randomly selected and rated using a fidelity assessment rating form in addition to being rated on the ENACT. A fidelity score will be calculated based on the proportion of key intervention components delivered as intended across the interactions based on these ratings.

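### In the stepped-wedge trial every CHW's only untrained ENACT roleplay is also the first one, so ENACT change should be reported as a before-after change and not as the effect of training

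*Combined protocol and SAP*

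**What the plan says.** The combined protocol and SAP sets the stepped-wedge roleplays as follows.

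- **Baseline (Section 3.5.2b):** "The baseline assessment will consist of self-report questions". No roleplay is listed.
- **Pre-training (Section 3.5.2b):** "Immediately before their training, participants will complete a pre-training assessment". The roleplay first appears here: "All CHWs will also complete a brief (~10 minutes) role-play vignette with a staff member who is minimally involved in delivering the training".
- **Last day of training (Section 3.5.2e):** "participants will additionally do another roleplay on their last day of training, which will be rated using the ENACT".
- **3-month follow-up (Section 3.5.2d):** CHWs "answer additional questions about their perceived feasibility/acceptability of the training, and complete a roleplay for later ENACT coding".
- **6-month follow-up (Section 3.5.2d):** another roleplay for ENACT coding.

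Section 4.3.1 makes ENACT a secondary measure of CHW stigma, with two uses. One takes pre-training items as predictors of later items. The other follows individual items across the timepoints "to examine the effect of the training and supervision on CHW helping skills and the durability of CHW helping skills over time". For the second use it names no comparison group, practice term, alternate vignette forms or caveat.

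**The concern.** Section 3.2.2 describes the trial's comparison as two timepoints under treatment as usual (baseline and pre-training) against two after training. Self-reported stigma is measured at all four. ENACT has only one untrained measurement, and it is the CHW's first encounter with the task. Anyone who scores better on a second attempt because the format is now familiar will appear to have benefited from training.

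At stake is what the trial may conclude from ENACT, which Section 4.1.2 says yields a final stigma score. It is the only observed, rather than self-reported, stigma measure taken both before and after training. A reader who sees a training effect on ENACT in a stepped-wedge report will assume that it has the same control as the primary outcome. It does not.

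**Working it through.** The documents give no numerical result for ENACT, so there is no figure to reproduce. The check is whether a training effect can be estimated from the roleplay schedule.

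**Inputs.** 60 CHWs in three groups of about 20 (Sections 3.3.2a and 7); the roleplay schedule above; calendar months from the Section 7 timeline.

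| Roleplay | Status | Group 1 | Group 2 | Group 3 |
|---|---|---|---|---|
| 1, pre-training | untrained | month 5 | month 6 | month 7 |
| 2, last training day | trained | month 5 | month 6 | month 7 |
| 3, 3-month follow-up | trained | month 9 | month 10 | month 11 |
| 4, 6-month follow-up | trained | month 12 | month 13 | month 14 |

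**Step 1: counts.** 60 × 4 = 240 roleplays. The 60 untrained ones are all attempt 1. The 60 × 3 = 180 trained ones are all attempts 2 to 4. The indicators for a repeat roleplay and for a trained roleplay are the same column, with correlation 1.00.

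**Step 2: can the stagger help?** No month holds an untrained roleplay from one group and a trained roleplay from another. The first roleplays in months 5, 6 and 7 are all untrained first attempts, so comparing them between groups says something about calendar drift. It says nothing about practice.

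**Step 3: estimability.** The design matrix had CHW effects, a training indicator, calendar time (absent, linear or by month) and a practice term. The figure shown is the variance of the training effect in units of residual variance.

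| Practice term | No time term | Linear time | Month effects |
|---|---|---|---|
| none | 0.0222 | 0.0313 | 0.0333 |
| first versus later | not estimable | not estimable | not estimable |
| free effect per attempt | not estimable | not estimable | not estimable |
| linear in attempt | 0.0556 | 1.1667 | not estimable |

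Training is estimable only if practice is assumed absent or strictly linear in attempt number. In the linear case with linear time the variance rises by a factor of 1.1667 / 0.0313 ≈ 37.

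**Step 4: is an untrained repeat available elsewhere?** Section 3.5.2e says the initial-training measures are reused, and the pilot's pre-assessment had a roleplay. That was a single assessment before training, and Section 3.5.2b is specific that baseline is self-report. Pilot participants are excluded (Section 3.3.2a eligibility table), so they supply no practised-but-untrained roleplays.

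**Step 5: illustration of size.** Assume no training effect, a pure practice gain, SD 1, and a two-sided 0.05 paired test in 60 CHWs. The within-person correlation r is 0.3 (stated in Section 3.3.2a for the Social Distance Scale and borrowed here) or 0.5 (assumed).

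For one later roleplay against the first, SE = √(2(1 − r)/60), which is √(1.4/60) = 0.153 at r = 0.3 and √(1.0/60) = 0.129 at r = 0.5.

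| Assumed practice gain | p<0.05, r = 0.3 | p<0.05, r = 0.5 |
|---|---|---|
| 0.1 SD | 10% | 12% |
| 0.2 SD | 26% | 34% |
| 0.3 SD | 50% | 64% |

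For the mean of the three later roleplays against the first at r = 0.3, SE = √(0.7 × (1 + 1/3)/60) = 0.125. A simulation of 2,000 trials gave p<0.05 in 34%, 65% and 97% at practice gains of 0.2, 0.3 and 0.5 SD. The mean apparent training effect equalled the practice gain each time.

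**The case against.** **ENACT is secondary, in a pilot of preliminary effectiveness.** This stands. The Social Distance Scale is among the self-report measures taken at both baseline and pre-training, and this point does not touch it. The predictor analysis needs no baseline roleplay. Pilot status limits the weight of the point, but it does not make the causal phrase supportable.

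**Rehearsal is partly the intervention.** This stands in part. Roleplays are used in training, and supervision includes them in the initial pilot, so skill gained there can count as effect. Familiarity with the assessment roleplay cannot, and its first repeat comes within the training week. Whether the same vignette is reused is not stated.

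**The size is hypothetical.** This stands. Section 4.3.1 plans no paired test at 0.05 for ENACT, and the documents give no basis for any practice gain. The figures show what practice could do, not that it is material here.

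A reader might go further and infer that the stepped wedge gives ENACT no control of any kind. The documents do not support that: the staggered first roleplays carry some between-group information on calendar drift, and Section 3.2.2 plans a time adjustment. A reader might also take ENACT to be the only observed stigma measure. The fidelity checklist in Section 4.2 covers stigmatising language and behaviour too, though only at the 3-month follow-up. What is missing is specifically a practised-but-untrained comparison.

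**Conclusion.** The point holds in this limited form. On the written schedule, training and first-versus-later practice are completely confounded for ENACT, and Section 4.3.1 claims more than the schedule can identify. This conclusion rests only on the assessment schedule and needs no assumption about the size of practice. The bias equals whatever practice gain exists, which is unknown; the percentages are illustrative and depend on the assumed gains and correlations.

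A reader might infer that a baseline roleplay must be added and its untrained change subtracted. That does not follow. With a baseline roleplay for everyone, attempts 1–2 are all untrained and attempts 3–5 all trained, so training is still not estimable against a free effect per attempt. It becomes estimable only if practice levels off after the first attempt, in which case the gain from attempt 1 to 2 should not be deducted from later change. Subtraction instead assumes equal practice gains over unequal intervals.

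**What to change.** **Required.** In Section 4.3.1, replace the stated purpose of the item-level ENACT analysis with wording such as:

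*Change in ENACT items across the four roleplays will be described as a secondary before-after change within CHWs. No practised-but-untrained roleplay is available for comparison, so improvement may partly reflect repetition of the roleplay. It will not be reported as a stepped-wedge controlled effect of training.*

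The cost is a few lines of text and a weaker claim for ENACT. No procedure changes.

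**Optional, and not part of the required fix.** If baseline visits are still ahead, a roleplay could be added there.

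- It means 60 more recordings (240 to 300, or 25% more), each needing a staff member minimally involved in training, video and an independent rating.
- It lowers the correlation between repeat and trained from 1.00 to 0.61, and separates training only from a practice effect that levels off after the first attempt.
- It makes the pre-training roleplay a second attempt, which weakens its use as a model for first-contact screening of CHWs in Section 4.3.1.
- The untrained change should not simply be subtracted.

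The relabelling is needed for the schedule as written and does not depend on this choice.
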